12.4 Effectiveness Analyses

12.4.1 Analysis of Primary Effectiveness Endpoint(s)

The primary objective of this study is to assess performance of the soft contact lens when worn in an extended wear modality (ie, up to 6 nights of continuous wear) as compared to Biofinity soft contact lens.

The primary endpoint is VA with study lenses, collected by eye.

12.4.1.1 Statistical Hypotheses

No hypothesis testing of the primary effectiveness endpoint is planned.

12.4.1.2 Analysis Methods

Summary statistics will be provided.

Effective Date: 22-Aug-2018 Alcon - Business Use Only Protocol - Clinical Version: 4.0; Most-Recent; Effective; CURRENT **Document:** TDOC-0054559 Status: Effective Page 47 of 53

12.5 Handling of Missing Data

All data obtained in evaluable subjects/eyes will be used. No imputation for missing values will be carried out.

12.6 Safety Analyses

The safety endpoints are:

Document: TDOC-0054559 **Version:** 4.0; Most-Recent; Effective; CURRENT

Status: Effective Page 48 of 53

- AEs
- Biomicroscopy
- Device Deficiencies

There are no safety hypotheses planned in this study. The focus of the safety analysis will be a comprehensive descriptive assessment of occurrence of AE as well as the other listed parameters.

Descriptive summaries (counts and percentages) for ocular and nonocular AEs will be presented by Medical Dictionary for Regulatory Activities Preferred Terms. A listing containing details of the AEs will also be provided.

Each biomicroscopy parameter will be tabulated by its grade.

Frequency for each device deficiency category will be presented and a supporting listing will be provided.

13 DATA HANDLING AND ADMINISTRATIVE REQUIREMENTS

13.1 Subject Confidentiality

Printed By:

The Investigator must ensure that the subject's anonymity is maintained throughout the course of the study. In particular, the Investigator must keep an enrollment log with confidential identifying information that corresponds to the subject numbers and initials of each study participant. At the end of the clinical study, the Study Sponsor will collect a copy of the enrollment log *without any identifying subject information*. All documents submitted to the Study Sponsor will identify the subjects exclusively by number and demographic information. No other personally identifying information will be transmitted to the Study Sponsor.

Print Date:

Document: TDOC-0054559 **Version:** 4.0; Most-Recent; Effective; CURRENT

Status: Effective Page 49 of 53

Effective Date: 22-Aug-2018

13.2 Completion of Source Documents and Case Report Forms

The nature and location of all source documents will be identified to ensure that original data required to complete the CRFs exist and are accessible for verification by the site monitor, and all discrepancies shall be appropriately documented via the query resolution process. Site monitors are appointed by the Study Sponsor and are independent of study site staff.

If electronic records are maintained, the method of verification must be determined in advance of starting the study.

At a minimum, source documents include the following information for each subject:

- Subject identification (name, sex, race/ethnicity)
- Documentation of subject eligibility
- Date of informed consent
- Dates of visits
- Documentation that protocol specific procedures were performed
- Results of study parameters, as required by the protocol
- IP accountability records
- Documentation of AEs and other safety parameters (if applicable)
- Records regarding medical histories and the use of concomitant therapies prior to and during the study
- Date of study completion and reason for early discontinuation, if applicable

It is required that the author of an entry in the source documents be identifiable. Direct access to source documentation (medical records) must be allowed for the purpose of verifying that the data recorded on the CRF are consistent with the original source data.

Alcon - Business Use Only Protocol - Clinical

Document: TDOC-0054559 **Version:** 4.0; Most-Recent; Effective; CURRENT

Status: Effective Page 50 of 53

Effective Date: 22-Aug-2018

Only designated individuals at the site will complete the CRFs. The CRFs must be completed at regular intervals following the clinical study visit schedule. It is expected that all data reported have corresponding entries in the source documents. The Principal Investigator is responsible for reviewing and certifying that the CRFs are accurate and complete.

13.3 Data Review and Clarifications

A review of CRF data to the subject's source data will be completed by the site monitor to ensure completeness and accuracy. After the CRFs have been completed, additional data clarifications and/or additions may be needed as a result of the data cleaning process. Data clarifications are documented and are part of each subject's CRF.

13.4 Sponsor and Monitoring Responsibilities

The Study Sponsor will designate a monitor to conduct the appropriate site visits at the appropriate intervals according to the study monitoring plan. The clinical investigation will be monitored to ensure that the rights and well-being of the subjects are protected, the reported data are accurate, complete, and verifiable from the source documents, and the study is conducted in compliance with the current approved protocol (and amendments[s], if applicable), with current GCP, and with applicable regulatory requirements.

[figure not shown]
The site may not screen subjects or perform the informed consent process on any subject until it receives a notification from an appropriate Study Sponsor representative that the site may commence conducting study activities. Monitoring will be conducted periodically while the clinical study is ongoing. Monitoring methods may include site visits, telephone, written and fax correspondence. Close-out visits will take place after the last visit of the last subject at the site.

A Coordinating Investigator may be identified by the Study Sponsor to review and endorse the final study report. In cases where a Coordinating Investigator is engaged, the Study Sponsor will select the Coordinating Investigator based upon their experience, qualifications, active study participation, and their willingness and availability to take on this role.

Document: TDOC-0054559 **Version:** 4.0; Most-Recent; Effective; CURRENT

Status: Effective Page 51 of 53

Effective Date: 22-Aug-2018

13.5 Regulatory Documentation and Records Retention

The Investigator is required to maintain up-to-date, complete regulatory documentation as indicated by the Study Sponsor and the Investigator's files will be reviewed as part of the ongoing study monitoring. Financial information is to be kept separately.

Additionally, the Investigator must keep study records and source documents consistent with the terms of the clinical study agreement with the Study Sponsor. If the Investigator retires, relocates, or for any other reason withdraws from responsibility of keeping the study records, then the Study Sponsor must be notified and suitable arrangements made for retention of study records and source documents needed to comply with national and international regulations.

13.6 Quality Assurance and Quality Control

The Study Sponsor will secure agreement from all involved parties to ensure direct access to all study related sites, source data and documents, and reports for the purpose of monitoring and auditing by the Study Sponsor, and inspection by domestic and foreign regulatory authorities. Quality control will be applied to each stage of data handling to ensure that all data are reliable and have been processed correctly. Agreements made by the Study Sponsor with the Investigator/Institution and any other parties involved in the clinical study will be provided in writing as part of the protocol or as a separate agreement.

14 ETHICS

This clinical study must be conducted in accordance with the ethical principles contained within:

- The Declaration of Helsinki, and in compliance with the ICH E6 GCP Consolidated Guideline, ISO 14155:2011, and the applicable US FDA 21 CFR Regulations.
- SOPs of the Study Sponsor and contract research organizations participating in the conduct of the clinical study and all other applicable regulations.

Document: TDOC-0054559 **Version:** 4.0; Most-Recent; Effective; CURRENT

Status: Effective Page 52 of 53

 Notifications and timelines for reporting protocol deviations should be based upon applicable Ethics Committee requirements

The Investigator must ensure that all personnel involved in the conduct of the study are qualified to perform their assigned responsibilities through relevant education, training, and experience. The Investigator and all clinical study staff must conduct the clinical study in compliance with the protocol. Deviations from this protocol, regulatory requirements and/or GCP must be recorded and reported to the Sponsor prior to database lock. If needed, corrective and preventive action should be identified, implemented, and documented within the study records. Use of waivers to deviate from the clinical protocol is prohibited.

Before clinical study initiation, this protocol, the informed consent form, any other written information given to subjects, and any advertisements planned for subject recruitment must be approved by an IRB/IEC. The Investigator must provide documentation of the IRB/IEC approval to the Study Sponsor. The approval must be dated and must identify the applicable protocol, amendments (if any), informed consent form, assent form (if any), all applicable recruiting materials, written information for subject, and subject compensation programs. The IRB/IEC must be provided with a copy of the IB, any periodic safety updates, and all other information as required by local regulation and/or the IRB/IEC. At the end of the study, the Investigator must notify the IRB/IEC about the study's completion. The IRB/IEC also must be notified if the study is terminated prematurely. Finally, the Investigator must report to the IRB/IEC on the progress of the study at intervals stipulated by the IRB/IEC.

Voluntary informed consent must be obtained in writing from every subject and the process shall be documented before any procedure specific to the clinical investigation is applied to the subject. The Investigator must have a defined process for obtaining consent. Specifically, the Investigator, or their delegate, must explain the clinical study to each potential subject and the subject must indicate voluntary consent by signing and dating the approved informed consent form. The subject must be provided an opportunity to ask questions of the Investigator, and if required by local regulation, other qualified personnel. The Investigator must provide the subject with a copy of the consent form written in a language the subject understands. The consent document must meet all applicable local laws and provide subjects with information regarding the purpose, procedures, requirements, and restrictions of the study, along with any known risks and potential benefits associated with the IP and the study, the available compensation, and the established provisions for maintaining confidentiality of personal, protected health information. Subjects will be told about the voluntary nature of participation in the study and must be provided with contact information for the appropriate individuals should questions or concerns arise during the study. The subject also must be told that their records may be accessed by appropriate authorities and Sponsor-designated

Document: TDOC-0054559 **Version:** 4.0; Most-Recent; Effective; CURRENT

Status: Effective Page 53 of 53

personnel. The Investigator must keep the original, signed copy of the consent (file in subject's medical records) and must provide a duplicate copy to each subject according to local regulations.

# Statistical Analysis Plan CLL949-C005 / NCT03614130

#### **Full Title:**

# Statistical Analysis Plan CLL949-C005

Protocol Title: Clinical Performance of a Silicone Hydrogel Following Six

Nights of Extended Wear

Project Number:

Protocol TDOC Number: TDOC-0054559

Author:

Template Version:

**Approvals:** See last page for electronic approvals.

Job Notes:

This is the second revision (Version 3.0) of the Statistical Analysis Plan for this study.

Alcon - Business Use Only Statistical Analysis Plan
Document: TDOC-0055319
Status: Effective

Executive Summary:

Key Objectives:

The primary objective is to assess

of the
soft contact lens when worn in an extended wear modality (ie, up to 6 nights of continuous wear) as compared to Biofinity® soft contact lens.

## ${\bf Alcon - Business \ Use \ Only \ \ } {\bf Statistical \ Analysis \ Plan}$

**Document:** TDOC-0055319 **Version:** 1.0; CURRENT; Most-Recent; Effective

Status: Effective

## 1 Study Objectives and Design

## 1.1 Study Objectives

#### PRIMARY OBJECTIVE

The primary objective is to assess

contact lens when worn in an extended wear modality (ie, up to 6 nights of continuous wear) as compared to Biofinity soft contact lens.

## 1.2 Study Description

Key components of the study are summarized in Table 1-1.

Table 1-1 Study Description Summary

Study Design	Prospective, randomized, controlled, double-masked, contralateral		
Study Population	Volunteer subjects aged 18 or over who are soft contact lens		
	wearers, excluding Biofinity habitual wearers, have at least		
	3 months of contact lens wearing experience, and who wear their		
	habitual lenses at least 5 days per week and in an extended wear		
	modality a minimum of 1 night per week.		
	. Pregnant		
	and breastfeeding women are excluded from this study.		
	Target to complete: 20; Planned to enroll: ~22		
Number of Sites	~2 (US)		
Test Product	soft contact lenses (LID011121)		
Control Product	Biofinity® (comfilcon A) soft contact lenses		
Duration of Treatment	Approximately 6 nights of extended wear		
Visits	Visit 1, Day 1: Baseline/Dispense		
	Visit 2, Day 2: 1-Day Follow-Up [24 hours (±4 hours) after Visit 1]		
	Visit 3, 1 Week: 1-Week Follow-Up/Exit [7 days (-1 day) after		
	Visit 2]		

#### 1.3 Randomization

A member of the Randomization Programming group at Alcon who is not part of the study team will generate the randomized allocation schedule(s) for study lens assignment.

Version: 1.0; CURRENT; Most-Recent; Effective

Effective Date: 25-May-2018

Status: Effective

Document: TDOC-0055319

Subjects will be randomized in a 1:1 ratio to receive and Biofinity contralaterally in one of the sequences below:

Sequence 1: (OD) / Biofinity (OS) Sequence 2: Biofinity (OD) / (OS)

#### 1.4 Masking

This study is double-masked.

#### 1.5 Interim Analysis

There are no plans to conduct an interim analysis and no criteria by which the study would be terminated early based upon statistical determination.

#### 2 Analysis Sets

### 2.1 Safety Analysis Set

Safety analyses will be conducted using the safety analysis set on a treatment-emergent basis. As such, the safety analysis set will include all eyes exposed to any study lenses evaluated in this study. For treatment-emergent safety analyses, eyes will be categorized under the actual study lens exposed at the time of the clinical assessment.

# 3 Subject Characteristics and Study Conduct Summaries

Demographic information (age, sex, ethnicity, and race) and habitual lens information will be tabulated.

**Document:** TDOC-0055319 **Version:** 1.0; CURRENT; Most-Recent; Effective

Status: Effective

#### 4 Effectiveness Analysis Strategy

This study defines one primary endpoint

Analysis Set will serve as the primary set for all effectiveness analyses.

The Safety

All data obtained in evaluable subjects/eyes will be included in the analysis. No imputation for missing values will be carried out for the primary analysis.

Effective Date: 25-May-2018

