12.1 Subject Evaluability

Final subject evaluability must be determined prior to breaking the code for masked treatment (lens sequence) assignment and locking the database, based upon the Deviations and Evaluability Plan.

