12.2 Analysis Sets

Only 1 analysis set will be defined, namely the safety analysis set. It will include all eyes exposed to any study lenses evaluated in this study.

Eyes will be analyzed based upon the lens exposed at the time of the clinical assessment.

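### Does the undefined word *evaluable* narrow the all-exposed-eyes set for the primary visual acuity summary?

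*SAP*

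**What the plan says.** Both documents declare one population. Protocol 12.2 states "Only 1 analysis set will be defined, namely the safety analysis set", and SAP 2.1 says that "the safety analysis set will include all eyes exposed to any study lenses evaluated in this study". SAP section 4 applies this set to effectiveness: the Safety "Analysis Set will serve as the primary set for all effectiveness analyses". Protocol 12.2 also fixes how eyes are attributed to lenses: "Eyes will be analyzed based upon the lens exposed at the time of the clinical assessment".

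A second term appears in the data-use sentences. SAP section 4 says "All data obtained in evaluable subjects/eyes will be included in the analysis" and continues "No imputation for missing values will be carried out for the primary analysis". Protocol 12.5, whose subject is missing data, says "All data obtained in evaluable subjects/eyes will be used" and likewise rules out imputation.

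The term is tied to a process in Protocol 12.1. Final subject evaluability must be settled before the lens-sequence code is broken and before "locking the database, based upon the Deviations and Evaluability Plan". That plan is a separate document. The visible glossary and abbreviation list have no entry for the term.

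Protocol 12.4.1.1 and SAP 4.2 plan no hypothesis test of the primary endpoint. SAP 4.3.1 reports Snellen counts and percentages and logMAR summary statistics at each visit.

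**The concern.** Exposure is a fact that needs no masked determination, whereas Protocol 12.1 makes evaluability a formal decision under a plan whose title links it to protocol deviations. So the word is not obviously a synonym for exposed. With only one analysis set declared, the visible text gives that decision no use except through the data-use sentences. A programmer could therefore apply it as a filter on the primary VA table.

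Two features of the trial sharpen the point. The design is contralateral, so dropping one eye breaks a within-subject pair. Protocol 12.1 speaks of subjects, while Protocol 12.5 and SAP section 4 speak of subjects or eyes. Also, SAP 5.3 applies the safety set to the safety tables without the word evaluable, so effectiveness and safety tables carrying the same set label could have different denominators. The primary result consists only of counts, percentages and means, so whichever eyes are counted determine what is reported.

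**Working it through.** The question is mainly textual, so the sentences are compared first.

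| Place | What it does | Does it remove an exposed eye? |
|---|---|---|
| Protocol 12.2, SAP 2.1 | Defines the only analysis set: exposed eyes | No |
| SAP 4, population sentence | Makes that set primary for effectiveness | No |
| SAP 4, data-use sentence; Protocol 12.5 | Says data obtained are used, next to the no-imputation rule | Not stated; worded to include |
| Protocol 12.1 | Times the evaluability decision and names the governing plan | Not stated |

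Three things follow.

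1. Only one population is declared, and it is named for effectiveness in the same SAP section as the doubtful sentence. The visible text contains no second rule for selecting eyes.
2. In both documents the doubtful sentence stands beside the statement that nothing is imputed. Its natural job is to say that observed values are used and gaps stay gaps.
3. Whether evaluability excludes any eye depends wholly on the Deviations and Evaluability Plan. Its absence from the review set is not a gap in the protocol or SAP.

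**Scale, if eyes were left out**

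Inputs: SAP Table 1-1 gives 20 to complete and about 22 to enrol, an allowance of 1 − 20/22 = 9.1%. The concern disputes neither figure. With one eye per lens per subject, take n = 20 to 22 eyes per lens. Assumed, because the documents do not give them: k = 1 or 2 eyes left out of one lens's summary, each differing by d = 0.1 to 0.2 logMAR from the mean of the rest.

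Shift in the lens mean = k × d / n:

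- k = 1: from 0.1/22 = 0.0045 to 0.2/20 = 0.0100 logMAR.
- k = 2: from 2 × 0.1/22 = 0.0091 to 2 × 0.2/20 = 0.0200 logMAR.

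At an assumed 0.1 logMAR per line, these are 0.045 to 0.10 line and 0.091 to 0.20 line. The direction is open: the mean improves if worse-seeing eyes are left out and worsens if better-seeing eyes are.

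Change in a Snellen category that holds c of n eyes, including the one left out:

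c/n − (c − 1)/(n − 1) = (n − c)/(n(n − 1)), which is largest at c = 1, where it equals 1/n.

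- One eye: at most 1/22 = 4.5 to 1/20 = 5.0 percentage points.
- Two eyes: at most 2/22 = 9.1 to 2/20 = 10.0 percentage points.
- Example: a category holding every eye but the one left out goes from 21/22 = 95.5% to 21/21 = 100%.

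Nothing in the documents supports any particular k or d. The two-line decrease in Protocol section 10 is a change within one eye from the Dispense Visit that the investigator should explain. It is not a gap between one eye and the mean of the others, so it does not justify d = 0.2. These figures show scale only; they do not estimate an error.

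**The case for a change.** The strongest case for a change is that the rule ought to be explicit. Protocol 12.1 describes a real decision process, and the visible text never says what hangs on it. With about 22 eyes per lens, a single omission shows in a percentage, and a short edit to SAP section 4 would remove the doubt.

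Part of this stands. The word is undefined in the visible text, the shift between subject and eye is untidy, and a cross-reference would help a reader. What does not stand is the step from an undefined word to a defective analysis. The declared set supplies the denominator, and an analyst who follows it has a complete instruction. Evaluability is decided before the code is broken, so exclusions could not be chosen with knowledge of the lens.

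A firm edit also has a cost. A statement that evaluability never removes an exposed eye from the VA summary would settle an unknown in one direction, and might override a prespecified plan that has not been read here. The parallel edits to Protocol 12.1 and 12.5 would need an amendment under Protocol section 4. Protocol section 12 already provides that departures from the analysis plan are handled by amendment or described in the clinical study report. That would cover an exclusion from the declared set, though not one the sponsor believed the evaluable wording allowed.

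**Conclusion.** No change to the plan is called for. This is loose wording that an analyst resolves sensibly from the text: use all available VA data from exposed eyes, by the lens worn at the assessment, with no imputation. On that reading the effect is zero. It would differ only if the Deviations and Evaluability Plan excluded exposed eyes. Even then, under the assumed k and d, the lens mean would move by about 0.005 to 0.020 logMAR for one or two eyes, and no test, margin or power would be touched.

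The conclusion rests on the visible text alone. Parts of both documents are blacked out, so a definition may sit in text that cannot be seen, and the separate plan was not available. Neither limitation shows an error in the protocol or the SAP.

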## 4.1 Effectiveness Endpoints

#### **Primary Endpoint**

The primary endpoint is distance visual acuity (VA) with study lenses, collected in Snellen, for each eye. Conversion will be made to the logMAR scale.

Version: 1.0; CURRENT; Most-Recent; Effective

Effective Date: 25-May-2018

Status: Effective

